10.4.4 Guidelines for reporting adverse events of special interest

10.4.4.1 AESI with immediate notification:

For these AEs, the Sponsor will be informed immediately (ie, within 24 hours), as per SAEs notification described in Section 10.4.3, even if not fulfilling a seriousness criterion, using the corresponding screens in the e-CRF.

- ALT≥3 ULN (if baseline ALT<ULN) Or ALT≥2 times the baseline value (if baseline ALT≥ULN) (Please refer to related flowchart in Appendix C). Baseline to be considered is the baseline of the current study.
- Allergic events
 - Allergic drug reactions and/or local injection site reactions deemed to be allergic (or have an allergic component) that require consultation with another physician for further evaluation of hypersensitivity/allergy, as per the investigator's medical judgment or as per Section 10.6.2, should be reported as an AESI with immediate notification.
 - All allergic events, and all injection site reactions having an allergic component or deemed to be allergic, require completion of the specific e-CRF screen (see Section 10.6.2), regardless of requirements for immediate reporting.
- Hemolytic anemia (See Section 10.4.5.1 and Appendix D)
 - If there is a decrease in hemoglobin and reflexive testing as per Appendix D suggesting hemolysis, then report this as an AESI with immediate notification. Special e-CRF screen will need to be completed.
- Pregnancy
 - Pregnancy occurring in a female patient included in the clinical trial.
 - Pregnancy will be recorded as a pre-specified AE with immediate notification in all cases. It will be qualified as an SAE only if it fulfills the SAE criteria.
 - IMP should be discontinued.
 - The follow-up of the pregnancy will be mandatory until the outcome has been determined.
 - Pregnancy occurring in the partner of a male patient included in the clinical trial. If permitted by the female partner and by local regulatory policies,

- Pregnancy will be recorded as a pre-specified AE with immediate notification in all cases. It will be qualified as an SAE only if it fulfills the SAE criteria.
- The follow-up of the pregnancy will be mandatory until the outcome has been determined.
- Symptomatic Overdose with IMP

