10.4.5.1 Hemoglobin decrease

At the first post-inclusion occurrence of a hemoglobin (Hb) measurement decrease by ≥1.5 g/dL as compared to the first visit (in the current study) hemoglobin measurement, then the Central Lab will reflexively measure haptoglobin using specimens already obtained at the same time point for which the hemoglobin decrease was detected. The Central Lab will provide the results of the reticulocyte count, haptoglobin, LDH and indirect bilirubin [reflexively measured only if the total bilirubin >ULN] to the investigator (see Appendix D).

- If the following pattern of abnormalities is noted:
 - Reticulocyte count >Central Lab's upper limit of the reference range (also referred to as ULN) AND
 - Haptoglobin < Central Lab's lower limit of the reference range (also referred to as LLN) AND
 - LDH>ULN AND
 - Indirect bilirubin >ULN (only if the total bilirubin >ULN),

- The patient should be referred to a hematologist. The hematologist should obtain a peripheral blood smear and anti-erythrocyte antibodies (direct and indirect) by Coombs test. Further investigations are at the discretion of the hematologist.
- If the results are normal or the pattern of abnormality is something other than that described above, then the Investigator should exercise his/her medical judgment in the interpretation of the results, necessity for workup of the decrease in hemoglobin or referral to a hematologist.

If a second hemoglobin measurement demonstrating a further decrease of ≥ 1 g/dL from the last available value is observed, even if the previous work-up was negative, the same investigations can be repeated and a hematology consultation can be requested at the discretion of the Investigator or at the Sponsor's request.

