11.4.2.1 Adverse events

Adverse event incidence tables will present by system organ class (SOC) (sorted by internationally agreed order), high-level group term (HLGT), high level term (HLT) and preferred term (PT) sorted in alphabetical order, the number (n) and percentage (%) of patients experiencing an AE. Multiple occurrences of the same event in the same patient will be counted only once in the tables within a treatment phase. The denominator for computation of percentages is the safety population.

Adverse event incidence table will be provided for all types of TEAEs: all TEAEs, all treatment emergent AESI, all treatment emergent SAEs and all TEAEs leading to permanent treatment discontinuation.

If any clinically significant signal is detected and need further characterization or for adverse event of clinical interest, exploration of time to onset could be performed for these selected TEAEs as described below to account for the differential exposure time in all patients. Selected TEAEs will be also analyzed using time-to-event approach (Kaplan-Meier methodology). Time from the first dose of IMP injection to the first occurrence of the event will be calculated (only the first event will be counted). Patients without any event will be censored at the end of the TEAE period. Incidence rates at different time points of exposure will be presented and Kaplan-Meier curves will be provided.

Death:

The following deaths summaries will be generated:

- Number (%) of patients who died by study period (TEAE, on-study, post-study) summarized on the safety population
- TEAE leading to death (death as an outcome on the AE CRF page as reported by the Investigator) by primary SOC, HLGT, HLT and PT showing number (%) of patients sorted by internationally agreed order of SOC and alphabetic order of HLGT, HLT, and PT.

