# Adverse events of special interest

AESIs are AEs (serious or non-serious) that need to be monitored, documented, and managed in a pre-specified manner described in the protocol. In this study, AESIs are the following (their complete descriptions are provided in the protocol):

- Local injection site reactions, selected using e-CRF specific tick box on the AE page;
- Allergic events:
  - General allergic events will be tabulated. Events will be selected using standardized MedDRA query (SMQ) "hypersensitivity" (broad and narrow) excluding the following preferred terms linked to local injection site reactions ("infusion site dermatitis", "infusion site hypersensitivity", "infusion site rash", "infusion site urticaria", "injection site dermatitis", "injection site hypersensitivity", "injection site rash", "injection site urticaria" and "injection site vasculitis");
  - General allergic events and local allergic reactions at IMP injection site will be described. This selection will be based on the above selection for general allergic event and on the following selection of PT from the symptoms complementary form for local injection site reaction ("Injection site dermatitis", "Injection site hypersensitivity", "Injection site oedema", "Injection site rash", "Injection site urticaria", "Injection site dermatitis", "Infusion site hypersensitivity", "Infusion site oedema", "Infusion site rash", "Infusion site urticaria", "Infusion site swelling");
- ALT≥3 ULN (if baseline ALT < ULN) or ALT ≥2 times the baseline value (if baseline ALT ≥ ULN), selected using laboratory data; The baseline that will be considered will be the OLE baseline of the current study
- Hemolytic anemia, selected using e-CRF specific tick box on the AE page and confirmed final diagnosis provided in the AE complementary form;
- Neurologic events selected using SMQs "demyelination" (broad and narrow), "peripheral neuropathy" (broad and narrow), and "Guillain-Barre syndrome" (broad and narrow) excluding the following preferred terms "acute respiratory distress syndrome", "asthenia", "respiratory arrest" and "respiratory failure";
- Neurocognitive events, selected using a company MedDRA query (CMQ), based on the following 5 HLGTs: "deliria (including confusion)", "cognitive and attention disorders and disturbances", "dementia and amnestic conditions", "disturbances in thinking and perception", and "mental impairment disorders";

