- Neurocognitive events, selected using FDA proposed grouping including the PTs "Amnesia", "Amnestic disorder", "Anterograde Amnesia", "Behavioural and Psychiatric Symptoms of Dementia", "Change in sustained attention", "Cognitive Disorder", "Confusional State", "Delirium", "Dementia", "Dementia Alzheimer's type", "Dementia

with Lewy Bodies", "Disorientation", "Disturbance in attention", "Executive dysfunction", "Frontotemporal Dementia", "Illogical Thinking", "Impaired reasoning", "Incoherent", "Judgement impaired", "Memory Impairment", "Mental Impairment", "Mental Status Changes", "Mini Mental Status Examination Abnormal", "Presenile Dementia", "Retrograde Amnesia", "Senile Dementia", "Thinking Abnormal", "Transient Global Amnesia", "Vascular Dementia" and the LLTs "Mental State Abnormal Aggravated", "Thinking Slowed";

- Ophthalmologic events selected using SMQs "optic nerve disorders" (broad and narrow), "retinal disorders" (narrow), and "corneal disorders" (narrow);
- Overdose with IMP (symptomatic or asymptomatic), selected using appropriate MedDRA codes and the tick box "Overdose with IMP" in the AE complementary e-CRF form;
- Pregnancy of female patient/subject (including male subject's partner) selected using appropriate MedDRA codes.

Analyses of allergic, neurologic and ophthalmologic events will also be provided using the tick box on the e-CRF AE page as a second approach.

In addition the following grouping of events will be provided:

- Hepatic disorder events using SMQ "Hepatic disorder";
- Diabetes mellitus or diabetic complications using HLGT "Diabetes Complications" and HLT "Diabetes Mellitus", HLT "Carbohydrate tolerance analyses (incl diabetes)" excluding PT "Blood glucose decreased" and including PT "hyperglycemia".

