# • Hematology:

- Red blood cells and platelets: hemoglobin, hematocrit, erythrocytes count, platelets count, reticulocyte count, red blood cell distribution width (RDW).
- White blood cells: white blood cell count, neutrophils, lymphocytes, monocytes, basophils, eosinophils.

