# Analysis of groupings of adverse events including selected adverse events of special interest

All grouping of TEAEs including adverse events of special interest as listed in Section 2.1.4.1 will be analyzed using selections defined in Section 2.1.4.1 and will be presented by SMQ and PT (when selection is based on SMQs) and by SOC and PT (when selection is based on the e-CRF tick box or HLGT/HLT). The summaries will be sorted by decreasing incidence of PT within each SOC/SMQ.

- Analyses of grouping of AEs for diabetes will be performed overall and according to the diabetic status at baseline.
- Serious TEAEs by PT for each grouping of AEs of special interest;
- TEAE(s) leading to permanent treatment discontinuation by PT for each grouping of AEs of special interest.

In addition, the following variables will be tabulated for the local injection site reactions TEAEs:

- Intensity of the event (mild, moderate, severe);
- Number of events divided by the number of OLE IMP injections received;
- Time from first OLE IMP injection to first injection site reaction;
- Description of the highest intensity of each symptom recorded in the specific e-CRF page with table and bar chart.

Besides, description of symptoms and possible etiologies for General Allergic Reaction TEAE reported by investigator (using the tick box), will be presented.

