# 2.4.5.3 Analyses of laboratory variables

The summary statistics (including number, mean, median, Q1, Q3, SD, minimum and maximum) of all laboratory variables (central laboratory values and changes from baseline) will be calculated for each visit or study assessment (baseline, each post-baseline value of the treatment period, last on-treatment and worst on-treatment value). In addition, for some parameters of interest, mean changes from baseline with the corresponding SE could be plotted over time (at same time points). This section will be organized by biological function as specified in Section 2.1.4.3. For glucose, only fasting samples will be summarized.

The incidence of PCSAs (list provided in Appendix A), as well as ALT increase as defined as AESI and hemoglobin decrease from baseline ≥15g/L, at any time during the TEAE period will be summarized by biological function irrespective of the baseline level and/or according to the following baseline status categories:

- Normal/missing
- Abnormal according to PCSA criterion or criteria

Glucose (quantitative summary and PCSA) will also be analyzed, overall and according to the diabetic status at baseline.

For parameters for which no PCSA criteria are defined, similar table(s) using the normal range could be provided.

Property of the Sanofi Group - strictly confidential

If any clinically significant signal is detected and need further characterization, exploration of time to onset will be performed for selected PCSAs assessed during the TEAE period as described below to account for the differential exposure time in all patients.

The incidence rates of selected PCSA during TEAE period at 24, 52, 78, 104 and 156 weeks of exposure will be calculated with Kaplan-Meier methodology, using the midpoint of the time interval between the first assessment with PCSA and the previous assessment. Kaplan-Meier curves will be also provided. Only the first event (PCSA) will be counted. Patients without any event will be censored at the last assessment performed during the TEAE period.

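### The hemolytic anemia row of the AESI tables counts only confirmed diagnoses, so it can fall short of the AESIs that the protocol has investigators report; the reported count should stand beside it

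*SAP*

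**What the plan says.** Protocol 10.4.4.1 lists hemolytic anemia among the AESIs with immediate notification: "If there is a decrease in hemoglobin and reflexive testing as per Appendix D suggesting hemolysis, then report this as an AESI with immediate notification". Protocol 10.4.5.1 gives the trigger, a first hemoglobin "decrease by ≥1.5 g/dL as compared to the first visit (in the current study) hemoglobin measurement, then the Central Lab will reflexively measure haptoglobin". If reticulocytes and LDH are high and haptoglobin is low (with indirect bilirubin also high where total bilirubin is raised), the patient is referred to a hematologist, who then obtains the smear and the Coombs test.

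On outputs, protocol 11.4.2.1 says: "Adverse event incidence table will be provided for all types of TEAEs: all TEAEs, all treatment emergent AESI, all treatment emergent SAEs".

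SAP 2.1.4.1 selects the event as "Hemolytic anemia, selected using e-CRF specific tick box on the AE page and confirmed final diagnosis provided in the AE complementary form". SAP 2.4.5.1 then states: "All grouping of TEAEs including adverse events of special interest as listed in Section 2.1.4.1 will be analyzed using selections defined in Section 2.1.4.1". At the end of the AESI list, SAP 2.1.4.1 adds: "Analyses of allergic, neurologic and ophthalmologic events will also be provided using the tick box on the e-CRF AE page as a second approach". Hemolytic anemia is not named there. On the laboratory side, SAP 2.4.5.3 provides that "hemoglobin decrease from baseline ≥15g/L, at any time during the TEAE period will be summarized by biological function". SAP 1.6 declares no statistical modification.

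**The concern.** The protocol has the AESI reported on a laboratory pattern, before the hematologist's work-up. The SAP counts it only after a final diagnosis has been confirmed. A patient can meet the first condition and not the second, because the work-up was inconclusive, the diagnosis was never entered, or it had not arrived by database lock.

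Safety is the primary objective, and the protocol treats this event as important enough for 24-hour notification and a dedicated e-CRF screen. A reader who sees zero in the row cannot tell from that row whether no case was reported or whether cases were reported and not confirmed. The serious-event and discontinuation summaries for each AESI grouping in SAP 2.4.5.1 use the same selection.

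**Working it through.** The plan states no figure to reproduce here. The check compares the text first, then sizes the effect.

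**1. The two rules side by side**

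| Step | Protocol report (10.4.4.1, 10.4.5.1) | SAP row (2.1.4.1) |
|---|---|---|
| Hemoglobin fall of at least 1.5 g/dL | needed | not mentioned |
| Reflex tests suggest hemolysis | needed, and then sufficient | not mentioned |
| Box ticked on AE page | follows from reporting (assumed) | needed |
| Confirmed final diagnosis | not needed | needed |

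The SAP joins its two conditions with 'and'. On the plain reading, a ticked case without confirmation fails the selection.

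**2. Where an unconfirmed case still shows**

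- All-TEAE tables by SOC, HLGT, HLT and PT (SAP 2.4.5.1): yes, under its coded term. That is a hemolysis term if the investigator's wording codes there, and something broader, such as anemia, if not. The table carries no AESI or tick-box flag.
- Hemoglobin decrease row (SAP 2.4.5.3): yes, if the fall is large enough. The thresholds agree: 1.5 g/dL × 10 = 15 g/L. SAP 2.4.5 runs such analyses on both the parent and the OLE baseline, and the OLE version corresponds to the protocol's comparison with the first visit. The row counts falls from any cause.
- Reflex tests: the red-cell and platelet list in SAP 2.1.4.3 is "hemoglobin, hematocrit, erythrocytes count, platelets count, reticulocyte count, red blood cell distribution width (RDW", and LDH and indirect bilirubin are under liver function. Three of the four elements are therefore listed singly. Haptoglobin is not listed, and no output combines the pattern.

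**3. Effect of one case on the row**

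- 1/1,200 = 0.083%, with 1,200 being the protocol's approximate maximum enrolment.
- 1/600 = 0.167%, with 600 treated as an assumption.

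As an illustration with 1,200 treated (exact 95% intervals, which the plan does not call for): 0 cases reads as 0% (0 to 0.31%), and 3 reported but unconfirmed cases (assumed) would read as 0.25% (0.05 to 0.73%) in a reported row.

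**4. When a diagnosis could be pending at lock**

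Let w be the weeks from sample to recorded diagnosis, which the documents do not give. SAP 4 sets lock at about 4 weeks after an interim cut-off. I assume that a diagnosis recorded before lock is used, in line with the SAP 3 rule on outcomes. A case is then pending only if its sample was taken less than (w − 4) weeks before cut-off. After Week 24, scheduled hematology is every 24 weeks. With visits spread evenly around the cut-off:

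| w (assumed) | Window before cut-off | Share of the 24-week interval |
|---|---|---|
| 4 weeks | 0 weeks | 0% |
| 8 weeks | 4 weeks | 4/24 = 17% |
| 12 weeks | 8 weeks | 8/24 = 33% |

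At the final analysis, take the last patient as a completer and the follow-up call as the last visit. The end-of-treatment visit is 2 weeks, and the call 10 weeks, after the last injection: 10 − 2 = 8 weeks, plus about 4 weeks to lock = 12 weeks. With ±7 days at both contacts the range is 6 + 4 = 10 to 10 + 4 = 14 weeks. Affected cases at that point would be mainly inconclusive or unrecorded diagnoses.

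**The case against.** The strongest reply is that a row named after a diagnosis should hold confirmed diagnoses. The protocol text can be read as telling the investigator when to report, not how to analyse. Reporting triggers and analysis selections differ for other AESIs too: neurologic and ophthalmologic events are reported on clinical judgment but selected mainly by standardized MedDRA queries. The tick-box second approach exists for groups whose first selection is MedDRA-based. Hemolytic anemia already uses its tick box, so its absence from that sentence need not be an oversight. All of this stands, and it is why the confirmed row should stay.

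A reader might infer that unconfirmed cases disappear from the report, or that no output could reveal them. The documents do not support that. A case coded to hemolysis or hemolytic anemia would be visible under that term in the all-TEAE tables and could be set against the AESI row. Protocol 10.5 commits the sponsor to reporting all safety observations in the study report, and 10.7 says that all events are included there. An independent DMC reviews accumulating safety data (6.4). AESIs are followed until they resolve or stabilise, or the patient dies (6.2.1).

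What remains after these safeguards is narrower. None of them commits to a count of reported hemolytic anemia AESIs next to the confirmed count, although protocol 11.4.2.1 promises a table of all treatment-emergent AESIs.

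**Conclusion.** The point holds as a minor reporting gap. The SAP row is narrower than the AESI that the protocol has investigators report, the narrowing is not declared, and no planned table flags the ticked but unconfirmed events as such.

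The number affected is not in the documents and may be zero. Each case changes the row by 0.08 percentage points with 1,200 treated, or 0.17 with an assumed 600. The 17% and 33% above are shares of a visit interval under assumed diagnosis times, for an interim analysis that is optional. They should not be read as the share of cases missed.

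Nor does the text support an inference that a safety signal is hidden or that the study's conclusion would change: the analysis is descriptive and no primary conclusion is shown to move.

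The conclusion assumes that 'and' in the SAP rule requires both conditions. Protocol Appendix D and the complementary form are not in the supplied text. If the form already separates confirmed from unconfirmed diagnoses, tabulating it may give the split directly.

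**What to change.** In SAP 2.1.4.1, keep the confirmed selection and add a second one: all treatment-emergent AEs with the hemolytic anemia box ticked, labelled *reported/suspected hemolysis*. Show both rows together, with ticked events lacking a confirmed diagnosis displayed as *not confirmed*. Split these into excluded and pending or unknown only if the complementary form records the difference.

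The cost is SAP wording and one or two table rows, using a tick box already on the AE page. No new samples, visits or staff are needed. The downside is that the reported row will include some patients who do not have hemolytic anemia, which the confirmed row beside it makes plain.

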#### 2.1.4.2 Deaths

The deaths observation period are per the observation periods defined above.

- Death on-study: deaths occurring during the on-study observation period
- Death on-treatment: deaths occurring during the treatment-emergent adverse event period
- Death post-study: deaths occurring after the last planned protocol visit

#### 2.1.4.3 Laboratory safety variables

Clinical laboratory data consist of blood analysis, including hematology and clinical chemistry. Clinical laboratory values will be analyzed primarily into international units and will also be analyzed into conventional (US) units when applicable.

Unless otherwise specified below, blood samples for clinical laboratories were to be collected at Visit 1 (Week 0), Visit 3 (Week 8), Visit 5 (Week 24), Visit 7 (Week 48), Visit 9 (Week 72), Visit 11 (Week 96), Visit 13 (Week 120), Visit 15 (Week 144) and Visit 17 (Week 168)/or early termination. The laboratory parameters (excluding those considered as efficacy parameters) will be classified as follows:

# • Hematology:

- Red blood cells and platelets: hemoglobin, hematocrit, erythrocytes count, platelets count, reticulocyte count, red blood cell distribution width (RDW).
- White blood cells: white blood cell count, neutrophils, lymphocytes, monocytes, basophils, eosinophils.

